3.12.2 Feasibility, acceptability, cost and safety outcomes

To determine feasibility we will collect data on numbers of eligible potential participants who are referred or self-refer for the study, the number of people who consent to participate and be randomised to either treatment and the number of people who remain in treatment and when people drop out and the number of people who remain in the research irrespective of whether they remain in treatment. We will calculate the cost of treatment by quantifying the number and duration of therapy sessions and by which therapist. This data will be collected by Inspire throughout the study duration using their Penelope data management system. We will include the cost of any patient safety measures used during treatment and up to the 20 week follow up point.

3.12.3 Health and Social Care Outcomes

We will assess health and social outcome using seven validated self-report questionnaires commonly used in mental health population studies. Data will be collected at baseline and 6, 12, 20 weeks and 52 weeks post-randomisation to assess participant burden, data quality and quantity and derive initial estimates of efficacy and effect size.

3.12.3.1 PTSD Symptoms

Post-traumatic stress disorder checklist for DSM-5 (PCL-5) (39, 67, 68) will be the likely primary outcome in our subsequent fully powered trial to assess symptoms of PTSD. The PCL-5 is a 20-item self-report measure that assesses the 20 *DSM-5* symptoms of PTSD. The PCL-5 has a variety of purposes, including monitoring symptom change during and after treatment, screening individuals for PTSD and making a provisional/probable PTSD diagnosis. The PCL-5 is a self-report measure that can be completed by patients in a waiting room prior to a session or by participants as part of a research study. It takes approximately 5-10 minutes to complete. Total PTSD symptom severity score (range - 0-80) is obtained by summing the scores for each of the 20 items. Preliminary validation work indicates a PCL-5 cut-off score of 33.

Evidence for the PCL for *DSM-IV* suggests that a 5-10 point change represents reliable change (i.e. change not due to chance) and a 10-20 point change represents clinically significant change (39). It was recommended to use 5 points as a minimum threshold for determining whether an individual has responded to treatment and 10 points as a minimum threshold for determining whether the improvement is clinically meaningful using the PCL for *DSM-IV*. In validation studies, the PCL-5 scores exhibited high internal consistency and the instrument was found to be a psychometrically sound measure of DSM–5 PTSD symptoms (69). The PCL-5 will be collected at the beginning of every therapy session in both groups. This data will be used to consider symptoms at the point of treatment attrition where this occurs and also contribute to operationalising the participant safety protocol (appendix 1).

3.12.3.2. Rehabilitation

The Work and Social Adjustment Scale (WSAS) (70) is a 5 item scale to assess the impact of the person's mental health on work, home, social and private leisure activities and interpersonal relationships. It has a 9-point assessment scale ranging from *Not at all* to *Very severely*. With internal scale consistency ranging from 0.7 to 0.9 and test-retest of 0.7 it is a valid and reliable scale for assessing impaired functioning in mental ill health (70).

3.12.3.3 Process of Recovery

The Quality of Process of Recovery scale (QPR) is a 15 item measure assessing recovery from psychosis or mental health problems and was collaboratively developed with service users (71). Since personal recovery self-defined and self-directed is something experienced rather than assessed by an expert, this self-report measure was deemed appropriate for this study as it reflects the wider aims of recovery including quality of life and social relationships. The questionnaire measures subjective recovery in two domains: intrapersonal functioning (17 items) and interpersonal functioning (five items). Each item is rated on a 5-point Likert scale ranging from 0 (Disagree strongly) to 4 (Agree strongly) with higher scores indicative of recovery. Respondents may score between 0 and 88. The subscales have good internal consistency and test–retest reliability over short periods. Cronbach's alpha coefficients for the intrapersonal and interpersonal scales for this sample were $\alpha = 0.94$ and $\alpha = 0.66$, respectively.

3.12.3.4 Emotional Distress

The Patient Health Questionnaire (PHQ) is a 9-item self-administered diagnostic instrument for depression. It scores each of the 9 mood-related DSM-IV criteria as "0" (not at all) to "3" (nearly every day) (72). Scores represent: 0-5 = mild, 6-10 = moderate, 11-15 = moderately severe, and 16-20 = severe depression. It is widely used to assess mood in UK general practice and IAPT services.

The General Anxiety Disorder (GAD 7) is a 7-item scale to assess for anxiety. It is used in primary care and mental health settings as a screening tool and symptom severity measure for the four most common anxiety disorders (Generalized Anxiety Disorder, Panic Disorder, Social Phobia and Post Traumatic Stress Disorder). Scores of 5, 10, and 15 are taken as the cut off points for mild, moderate, and severe anxiety, respectively. When used as a screening tool, further evaluation is recommended when the **score** is 10 or greater (73).

3.12.3.5 Health status

EQ5D-5L (74) is a two-page questionnaire with page consisting of the EQ-5D descriptive system and page 2 the EQ visual analogue scale (EQ VAS). Page one comprises five dimensions: mobility, self-care, usual activities, pain/discomfort and anxiety/depression. Each dimension has five levels: no problems, slight problems, moderate problems, severe problems and extreme problems. The participant indicates their health state by ticking the box next to the most appropriate statement in each of the

five dimensions. This decision results in a 1-digit number that expresses the level selected for that dimension. The digits for the five dimensions can be combined into a 5-digit number that describes the patient's health state. The EQ VAS records their self-rated health on a vertical visual analogue scale, where the endpoints are labelled 'The best health you can imagine' and 'The worst health you can imagine'. The VAS can be used as a quantitative measure of health outcome that reflect the patient's own judgement. The EQ-5D-5L has been validated in a diverse patient population in six countries including eight patient groups with chronic conditions. The measurement properties of EQ-5D-5L were superior to its predecessor EQ-5D-3L in terms of feasibility, ceiling effects, discriminatory power and convergent validity.

3.12.3.6 Health and social-services utilisation

FolATED (75) is a 31 item administered questionnaire or structured asking about number of contacts with general practice, social services, mental health services and other agencies during the past specified period. It is hosted by DIRUM, an open-access database of resource-use questionnaires for use by health economists involved in trial-based economic evaluations. Funded by the Medical Research Council Network of Hubs for Trial Methodology Research, DIRUM offers a unique (and permanent) web address for each resource use measure for citation in papers and reports. DIRUM also provides a repository of methodological papers related to resource use and cost measurement (76).

3.12.4 Acceptability of both treatments

Qualitative interviews will be undertaken with 20–30 participants from both RTM and TF-CBT groups. The interviews aim to determine the acceptability and feasibility of participating in the trial and the treatment they received. We will aim to interview 2-3 participants who chose to withdraw from the treatment, 2-3 who chose to withdraw from the trial and the remainder from those who completed the treatment and who completed at least the 12-week follow up. Interviews will be undertaken in a venue of the participant's choosing that is safe for the participant and the researcher. This could be face-to-face, over the telephone or online. Participants are asked to give specific consent to be approached for an interview on the consent form. Interviews will be analysed using thematic content analysis.

3.13 Data Collection

Socio-demographic and medical history variables will be obtained from Inspire's clinical records following the completion of eligibility, informed consent procedures, baseline data collection and diagnostic confirmation assessment. Each participant's demographic and medical history data will be entered onto the study database hosted on the King's College London secure server. Data will be entered by a researcher or a trained Inspire administrator and a participant identification number will be generated.

Feasibility, acceptability, cost and safety outcomes will be collected by the QUB researcher by monitoring when and why participants drop out of either intervention or the research study. Costs of therapy data will be recorded by both TF-CBT and RTM therapists based on £75.00 per session for the number, duration and location of therapy sessions per participant and collated by the researcher. Therapy location data will be collected to incorporate therapist travel into the delivery costs. The independent clinical psychologist will inform the researcher when any participant makes contact, the frequency and duration of these contacts and the outcome.

Health and Social Care Outcomes will be collected via a series of validated questionnaires. Following completion of informed consent procedures and prior to randomisation, baseline data will be

collected from the participant with follow up taking place at 6, 12, 20 and 52 weeks post randomisation. Data collection will be undertaken either in person (aligned to a therapy appointment where they coincide), over the telephone (with paper copies having been sent via post in advance), or electronically (by secure web data collection software or email). The participant can choose their preferred method at each follow up point. Paper questionnaires, with participant identifiers, will be scanned and sent via encrypted email from Queen's University Belfast to the King's College London Trial Manager. Electronically completed surveys will be sent by encrypted email in the same way. Data will be entered into a project specific eCRF database supported by KCTU and hosted on the KCTU server. Follow up data will be acceptable if it is completed/collected 10 working days either side of the official follow-up date at 6, 12 and 20 weeks and within one calendar month at 52 week follow up. Data arriving outside of these time period will be classed as missing for the purpose of analysis.

3.14 Statistical Data Analysis

We will calculate rates of recruitment, willingness to participate, proportions of participants with PTSD and complex PTSD, intervention and research drop-out rates. Estimates of variability (standard deviation) of outcome assessments will be used to inform the sample size calculation for the future fully powered non-inferiority RCT. We expect to use a non-inferiority margin for PCL-C of five. A similar conservative margin was proposed by Foa *et al* (2018) (77) for PCL-5 based on Monson *et al* (2008)(78). Prior to making this calculation the main study outcome(s) will be examined to see whether they conform reasonably well to a normal distribution. If not a transformation of the data will be considered. SAS procedure POWER (50) will be used to calculate the sample size estimate for a comprehensive follow-on non-inferiority RCT (42). Exploratory analyses will enable the standard deviation of changes in pilot outcome assessments to be calculated using appropriate statistical methods (e.g. random effects regression models).

Because the change of randomisation ratio took place mid-way through the trial when 50% of the target number of randomisations had already occurred on a 1:1 ratio, the analysis of participant data before (1:1 ratio) and following (2:1 ratio) the allocation change will need be undertaken separately.

The study will use King's CTU standardised operating procedures as appropriate, as follows:

- 1. Data monitoring committee
- 2. Statistical analysis plan
- 3. Statistical documentation retention
- 4. Statistical QA
- 5. Sample size calculation
- 6. Protocol review and blinding
- 7. Statistical reports
- 8. Data manipulation following data extraction

We will follow the CONSORT guidance for pilot and feasibility trials and for intervention studies and the TIDieR checklist (79, 80).

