Our charity partner, Inspire, will provide these treatments to study participants. People taking part will be randomly allocated to either TF-CBT or RTM therapy. Inspire have considerable experience and expertise in delivering psychological therapies to veterans with PTSD who served in Northern Ireland. Inspire therapists will be trained to deliver both interventions and will be supervised by experts in these therapies.

Within 28 months, we will:

- Train Inspire's therapists in TF-CBT and RTM treatments;
- Recruit and allocate 60 participants randomly to either treatment;
- Calculate how many veterans remain in the trial/treatment and understand reasons for drop-out;
- Collect questionnaire data at 6, 12, 20 and 52 weeks post randomisation;
- Determine the acceptability of the treatments and the research trial for participants and any barriers to participation.

Beneficiaries include:

- Inspire's therapists Upskilled through training in the two treatments;
- Veterans and their families Potential reduction in PTSD symptoms and identification of veteran and PTSD profiles for whom this treatment appears to work best/not work so effectively.
- Veterans, their families, Research Partners and wider mental health sector Knowing whether a larger trial of RTM is justified and, if so, how a larger trial might best be undertaken;

 Research Partners - Upskilled by research involvement. Increased visibility of services within the veteran community and beyond.

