3.11 Interventions

3.11.1 Therapy A: Experimental Group – RTM Protocol

The experimental intervention is the Reconsolidation of Traumatic Memories protocol (RTM), an NLP based, non-traumatising intervention (28, 31-33) delivered in up to 5 x 90 -120 mins weekly sessions by a single trained therapist. The RTM Protocol is a brief cognitive intervention with minimal and non-traumatizing exposure to the original stimulus. The RTM protocol effectively rewrites the emotional elements of the memory by taking advantage of the phenomenon of reconsolidation (51, 52). The procedure is manualized and fully described by Gray & Liotta (2012)(53). Reconsolidation describes the reactivation of long term, otherwise permanent memories, by their evocation in certain contexts. When a memory is reactivated, it labilises, that is, it becomes subject to change. If the circumstances surrounding the memory remain the same, the memory remains unchanged; it is maintained in its current state. If circumstances have intensified, the impact of the memory may become worse; retraumatization can add to the intensity of trauma memories. If the new circumstance provides evidence that a threat of negative emotional stimulus is no longer relevant, the strength of the affective charge may decrease.

The intervention proceeds as follows:

- 1. Evoke the trauma, with or without description (most NLP interventions can be completed content free).
- 2. Interrupt the re-emergence of the trauma as soon as the client begins to show physiological signs of its onset. Changes in breathing, skin colour, posture, pupil dilation and eye fixation are typical signs of memory access. As they appear, the state is to be broken by reorienting the client to the present, by changing the subject, redirecting their attention into a different sensory system, or firing off a pre-existing anchor. However it is accomplished, it is important to stop the development of the symptoms before they take control of the client's consciousness.
- 3. After a few minutes away from the trauma, ask the client to think of a time before the trauma when they were doing something pleasant in a safe, neutral context.
- 4. Instruct the client to imagine that they are sitting in a movie theatre and that they are watching that scene on the screen.

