3.11.2 Therapy B: Comparison Group – TF-CBT

Trauma-Focused Cognitive Behaviour Therapy delivered over up to 18 x 60-90 minute weekly sessions delivered by a single TF-CBT trained therapist (15). TF-CBT is the gold standard for treating PTSD and is currently the first line of treatment recommended by NICE for PTSD (15). Research evaluating TF-CBT in adults with PTSD has established an empirical base supporting the efficacy of the intervention(19, 54, 55). A substantial number of RCTs in England and Northern Ireland have established the efficacy of TF-CBT in PTSD(56-59). These RCTs have shown very large effect sizes in treating PTSD symptoms and associated symptoms of depression and anxiety. TF-CBT for PTSD is a face-to-face therapy of up to 12 x 60 to 90-minute sessions that involves identifying the relevant appraisals, memory characteristics and triggers, and behavioural and cognitive strategies that maintain PTSD symptoms.

The cognitive model of PTSD developed by Ehlers and Clark (2000) (60) will be the model used in this study as it displays the largest treatment effect sizes and significant symptom improvements (56, 57, 61) suggesting why it is widely carried out and recommended in IAPT services (62, 63). This cognitive theory of PTSD addresses these symptoms by:

(A) modifying excessively negative appraisals of the trauma and/or its sequelae in maintaining the symptomatology of PTSD,

(B) reducing re-experiencing by elaboration of the trauma memories and discrimination of triggers in the development of PTSD, and

(C) dropping dysfunctional behaviours and cognitive strategies, particularly those related to avoidance of triggers for intrusive symptoms.

These are strategies that have the immediate aim of reducing one's sense of current threat but have the long-term effect of maintaining the disorder and are common in PTSD.

TF-CBT in this study will be delivered in up to 18 x 60 to 90-minute sessions each as recommended by NICE. The course and delivery of TF-CBT in this study for veterans with simple PTSD proceeds as follows (for complex PTSD, the same delivery may take up to 18 sessions):

Session 1:	Treatment goals
	Normalisation of PTSD symptoms
	Identification of main intrusive memories
	• Initial identification of maintaining factors (appraisals, cognitive strategies
	such as thought suppression, rumination, hypervigilance, safety
	behaviours) and initial shared case formulation (to be revised throughout
	treatment)

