3.11.3 Therapists, their management and therapy training

Prior to training to deliver either intervention, Inspire employed psychological therapists will demonstrate the following:

- a. Minimum of a Diploma in Counselling/Psychotherapy from the BABCP or the BACP or UKCP as a minimum.
- a. Post-graduate CBT training meeting competency standards for accreditation with the BABCP.
- b. Minimum of three years' post-qualifying supervised clinical practice with trauma clients.
- c. Personal supervision records, reputable references, commitment to clinical supervision and on-going training.
- d. Professional indemnity insurance.
- e. Security cleared to Counter Terrorist Check level.

Psychological therapists delivering both interventions will continue to be managed by their employer, Inspire. In addition to the usual policies and practices of Inspire relating to clinical, information and financial governance, the therapists will receive project-specific professional development and support via their employer from EITHER table 1 or table 2.

Pre-trial assessment will be undertaken of candidate therapists by the RTM and the TF-CBT training leads. This will determine candidate therapist competency for undertaking the trial training. The training leads retain collaborative authority for selecting the trial therapists. This will reduce therapist variance across both arms. Therapists will complete a pre-training competency self-assessment (appendix 3) to include accreditations, qualifications and duration of experience in a therapeutic role. The trainers will together make assessments of the level of competency demonstrated on paper and allocate each therapist to 1 of 5 groups:

- Group A (level 1) consisted of newly accredited counsellors with limited experience of working with simple or complex PTSD, and a self-rating of competent across the majority of skills.
- Group B (level 1+) were counsellors who had been accredited for 5 years, including 5 years' experience of working with simple and complex PTSD. Self-rating spanned the competent and

proficient skills for generic counselling skills and novice or advanced beginner for CBT and NLP specific competencies.

- Group C (level 2) counsellors had minimum 8 years post accreditation experience and 9+ years' experience of working with simple and complex PTSD. Counsellors rated proficient in generic competencies and competent or proficient in CBT and NLP specific competencies.

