- Group D (level 2+) counsellors had minimum 11 years post accreditation experience, a post graduate qualification and 10+ years' experience of working with simple and complex PTSD. Counsellors rated proficient in generic competencies.
- Group E (level 3) counsellors had minimum 10 years post accreditation experience, rated expert in generic and NLP/CBT competencies and had an additional professional registration to that of counselling or psychotherapy.

Individual therapists in group A will be randomly assigned to intervention group 1 or group 2 by the trial statistician. This process will be repeated for individual therapists in groups B to E to result in two balanced therapist groups with an equivalent level of core competencies, skills and experience. *Table 1*

Therapy	A: RTM Protocol Training	Hours per
		therapist
1	Pre-course reading	4
2	Classroom teaching face to face by [name]	40
3	Successfully treat and undertake symptom assessments with 2 trauma patients with	4
	[name] observing therapy delivery live via skype and providing post therapy coaching	
	Clinical Supervision	
4	Clinical supervision, using a mix of individual and group, 90-minute sessions via skype, will be provided to each therapist by [name] [name]. Approximately 20 sessions of clinical supervision per therapist will be undertaken depending upon how many participants in therapy simultaneously. A minimum of 2 supervision sessions will be individual. Online clinical supervision by video conferencing is feasible and effective compared to face to face supervision and is widely used (64-66).	20-30 hours (90 mins every 2 weeks for 25 weeks then monthly for the remaining intervention delivery period.)
5	Expert observation and assessment by USA lead clinical psychologist (Total 8 hrs per therapist)	
6	Observing 2 sections of RTM therapy sessions via video recording per therapist	3
7	Assess and coach RTM therapist during 4 x 1 hour skype sessions per therapist	4
8	Provide final written assessment per therapist on therapist competence and protocol fidelity	1

Table 2

Therapy	B: TF-CBT Training	Hours per therapist
1	Classroom teaching face to face by an expert accredited in the Ehlers and Clark protocol (57) with experience in clinical care, education and research in testing the protocol. Therapists will learn, practice and have their competency assessed by the trainer.	24
2	Expert observation and assessment by expert TF-CBT trainer who undertook training.	

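### The planned main-trial sample-size calculation names no allowance for therapist clustering, although the pilot nests participants in therapists who each work in one arm

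*Protocol*

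**What the plan says.** **Therapist structure in the pilot.** RTM is given in "weekly sessions by a single trained therapist" (section 3.11.1) and TF-CBT in "weekly sessions delivered by a single TF-CBT trained therapist" (section 3.11.2). Section 3.11.3 says therapists receive "project-specific professional development and support via their employer from EITHER table 1 or table 2", that is, RTM or TF-CBT training. It adds that "Individual therapists in group A will be randomly assigned to intervention group 1 or group 2 by the trial statistician", with the same step repeated for groups B to E. Appendix 4 asks for at least 5 TF-CBT therapists and at least 5 different RTM therapists. The lay summary can be read the other way: "Inspire therapists will be trained to deliver both interventions and will be supervised by experts in these therapies".

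**Main-trial calculation.** Section 3.14 says: "Estimates of variability (standard deviation) of outcome assessments will be used to inform the sample size calculation for the future fully powered non-inferiority RCT". It expects a non-inferiority margin of five, and then: "SAS procedure POWER (50) will be used to calculate the sample size estimate for a comprehensive follow-on non-inferiority RCT". Random effects regression is mentioned only as an example of how to obtain the standard deviation of changes, and no random factor is named.

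**Data available.** Section 3.12.2 costs treatment by "quantifying the number and duration of therapy sessions and by which therapist", so therapist identity is recorded.

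**The concern.** Supporting the power calculation for the non-inferiority trial is objective 2 of the pilot (section 3.1) and Outcome 2 in Appendix 4. Patients of the same therapist tend to have more similar outcomes than patients of different therapists. When each therapist works in one arm only, that between-therapist variation does not cancel in the treatment comparison and adds to its variance. A two-sample calculation from a standard deviation and a margin treats participants as independent and leaves this component out.

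Selecting therapists on competency and balancing them across arms helps comparability, and selection may reduce between-therapist variance. Neither removes whatever within-therapist correlation remains. If the component is left out, the funding application that follows the pilot would ask for too few participants, and possibly too few therapists, for the intended power.

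**Working it through.** The protocol states no main-trial sample size, so there is no figure to reproduce.

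**Inputs from the protocol**
- Margin: 5 points (section 3.14).
- Pilot size: 60 participants (section 3.6).
- Therapists: at least 5 + 5 = 10 (Appendix 4).
- Participants per therapist: 60/10 = 6. If the first 30 are split 15:15 and the next 30 are split 20:10, the totals are 35 RTM and 25 TF-CBT, or 7 and 5 per therapist with 5 therapists per arm. Section 3.6 reports TF-CBT therapist attrition without numbers, so the caseload there may be higher.

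**Assumed, because the protocol gives no value**
- Therapist ICC 0.01 to 0.10.
- One-sided alpha 0.025, power 80% or 90%, true difference 0, 1:1 allocation.
- SD 20 for the worked size.
- The pilot's 6 participants per therapist carried into the main trial.

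**Step 1: size without clustering.** n per arm = 2·SD²·(z₀.₉₇₅ + z_power)²/margin².
- 80% power: 2·400·(1.960 + 0.842)²/25 = 251.2, so 252.
- 90% power: 2·400·(1.960 + 1.282)²/25 = 336.2, so 337.

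**Step 2: design effect.** DE = 1 + (m−1)·ICC. With m = 6 this is 1.05, 1.25 and 1.50 at ICC 0.01, 0.05 and 0.10.

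**Step 3: power if the size is not inflated.** Power = Φ((z₀.₉₇₅ + z_power)/√DE − 1.960). At DE 1.25 and nominal 80%: 2.802/1.118 − 1.960 = 0.546, and Φ(0.546) = 0.707.

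| ICC (m = 6) | DE | Nominal 80% becomes | Nominal 90% becomes | n per arm needed, SD 20 (80% / 90%) |
|---|---|---|---|---|
| 0.01 | 1.05 | 78% | 89% | 265 / 354 |
| 0.05 | 1.25 | 71% | 83% | 315 / 422 |
| 0.10 | 1.50 | 63% | 75% | 378 / 506 |

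The power columns do not depend on the assumed SD. With m = 10 and ICC 0.05, DE = 1.45 and the powers are 64% and 77%.

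**Step 4: does the pilot SD absorb the effect?** No. With k = 5 therapists of m = 6 per arm, the expected ordinary within-arm variance is 1 − ICC·(m−1)/(km−1) of the true total. At ICC 0.10 that is 1 − 0.10·5/29 = 0.983. The variance is slightly too low, not inflated.

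**Step 5: number of therapists.** Effective n per arm is km/DE, which cannot exceed k/ICC. With 5 therapists per arm the ceiling is 5/0.05 = 100, or 5/0.10 = 50. Beyond a point, only more therapists restore power.

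**Step 6: can the pilot supply the ICC?** Not reliably. In simulation with 5 therapists of 6 participants per arm and a true ICC of 0.05, the central 95% of ANOVA estimates ran from about −0.12 to 0.27.

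**The case against.** The strongest reply is that section 3.14 says nothing false. Standard deviations are to inform the calculation, SAS POWER is the tool, and neither rules out a later design-effect multiplier. The random effects models could carry a therapist term. The section also refers to trials-unit procedures for the analysis plan and for sample size, whose content is not shown. The main trial is not designed: section 4.1 directs it towards the NHS and a wider population, and its therapist numbers and caseloads are open. Therapist selection, supervision and fidelity checks may also keep the ICC low.

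Much of this stands, and it limits what can be claimed. A reader might infer that the main trial will certainly be under-sized. The protocol does not support that, because it gives no main-trial size, SD, alpha, power or therapist structure and does not exclude inflation. A reader might also infer that the main trial's type I error will be inflated, since a test ignoring clustering at DE 1.25 has one-sided error Φ(−1.960/1.118) = 4.0% instead of 2.5%. But section 3.14 does not describe that trial's analysis. Nor does it specify a between-arm standard error for the pilot. The lay summary, if read as each therapist delivering both therapies, conflicts with nesting in arm.

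The objection does not remove the omission. The protocol chose to name the inputs and the tool for one of its main outputs, while its own design creates the therapist layer. The result of those named steps is a size for independent participants.

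**Conclusion.** The concern holds as a gap in a calculation that the protocol specifies. The pilot nests participants in single therapists allocated to one arm, and section 3.14 sets out the main-trial calculation with no allowance for that. If it is followed as written and the main trial keeps a similar therapist structure, the projected size is too small for any positive therapist ICC with more than one participant per therapist.

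The direction follows from the design; the size does not. With 6 participants per therapist, the loss ranges from about 2 points of nominal 80% power at ICC 0.01, which is minor, to about 17 points at ICC 0.10. The ICC, alpha and power are all assumed, the caseload is carried over from the pilot, and the example sizes also assume SD 20. Nothing here questions the pilot's own sample size or conduct.

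**What to change.** In section 3.14, add to the SAS POWER step and do not replace it:

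- Treat the SAS POWER result as the individually randomised size, then multiply it by 1+(m−1)ICC, where m is the planned number of participants per therapist. State m and the number of therapists per arm.
- Show the result for planning ICCs of 0.01, 0.05 and 0.10, because about 10 pilot therapists cannot estimate the ICC reliably.
- Include a therapist random intercept in the exploratory outcome models, using the therapist identity already recorded under section 3.12.2.
- Reconcile the lay summary's statement on therapist training with section 3.11.3 and Appendix 4, so that it is clear whether therapists are nested in arm.

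The cost is some wording and a few lines of analysis code. The downside is a larger projected main trial, and possibly a need for more therapists. No extra pilot participants or data are required.
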